8.7.1. Efficacy Analysis

Progression-Free Survival (PFS)

Combined PFS of the SU-AXI sequence is defined as the time from when the patient receives the the first dose with SU in first line, until progression or death due to any cause with AXI in 2nd line, whichever occurs first during the SU-AXI sequence. PFS in patients receiving AXI in 2nd line is defined as the time from when the patient receives the first dose of AXI to the time of progression or death due to any cause, whichever occurs first.

Patients who remain progression free at the end of AXI treatment will be evaluated until death, disease progression or the start of a new anticancer therapy.

For the primary endpoints, PFS will be assessed using the Kaplan-Meier method. This method will be applied to derive, survival curves, median event time and a 95% confidence interval for the median.

Kaplan-Meier estimates will also be provided for sub-group analysis of interest:

- Titrated and non-titrated patients, defined in the following section (titration description section), receiving AXI in 2nd line
- Patients receiving AXI in 2nd line post SU depending on the response to SU in 1rst line.
- Country cohorts where feasible (pool size)
- SU 2nd groups depending on the 2nd line treatment :
 - O SU in 1st line- AXI in 2nd line,
 - o SU in 1st line other TKI in 2nd line (sorafenib, pazopanib)
 - O SU in 1st line / mTOR in 2nd line. (temsirolimus, everolimus)

Potential influences of baseline patient characteristics (eg, age, sex, MSKCC risk group) on the primary PFS will be evaluated by Cox proportional regression method.

Time to Treatment to Failure (TTF) and Time to Strategy Failure (TSF)

TTF for the AXI 2nd line is defined as from when the patient receives the first dose of AXI to the time of AXI discontinuation (date completed by the physician) whatever the reason for discontinuation is and whatever the following therapeutic strategy. In case of death while the patient is still treated with AXI, date of death will be considered as date of discontinuation.

TTF for the SU-AXI sequence is as defined as the time from when the patient receives the first dose with SU in first line to the time of AXI discontinuation (date completed by the physician).

TSF for SU-AXI sequence is defined as the time from when the patient receives the first dose with SU in first line to the time of AXI discontinuation (date completed by the physician) without the time between discontinuation of SU and start of AXI.

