The TTF will be defined as the time from when the patient receives the first dose of AXI to the date of AXI discontinuation (date completed by the physician), whatever the reason for discontinuation and whatever the following therapeutic strategy.

Variable name	Definition
TTF status	Patient will not be censored for the TTF analysis (TTF status = 1) in the following cases:
	 Axitinib discontinued due to Progression, Intolerability or Death (cf. CRF page 35)
	 Study Discontinuation for any reason except lost to follow-up or patient's request whereas last treatment received is Axitinib (cf. CRF page 37)
	In all other cases, patient will be censored for the TTF analysis (TTF status = 0).
	Note: Other reasons for Axitinib discontinuation as well as other reason for study discontinuation (whereas last treatment received is Axitinib) will be reviewed at time of DRMs in order to decide whether corresponding cases should be censored or not for TTF analysis
TTF time	The time to treatment failure will be calculated in months as:
(months)	• (Date of progression/intolerability or death reported at time of Axitinib discontinuation - Start date of Axitinib + 1) / 30.44, if case n°1 described above is reported
	 (Date of death reported on the Study Discontinuation form - Start date of Axitinib + 1) / 30.44, if case n°2 described above is reported and reason for study discontinuation is 'death'
	• (Axitinib end date reported on the Study Discontinuation form - Start date of Axitinib + 1) / 30.44, if case n°2 described above is reported and reason for study discontinuation is not 'death' and Axitinib status at last visit is 'discontinued'
	Note: as only month and year of Axitinib end are reported in such cases, day of Axitinib end will automatically be "forced" to 01
	• (Last visit date reported on the Study Discontinuation form - Start date of Axitinib + 1) / 30.44, if case n°2 described above is reported and reason for study discontinuation is not 'death' and Axitinib status at last visit is 'ongoing'
	• (Minimum of {Date of progression/intolerability or death reported at time of Axitinib discontinuation ; Date of death reported on the Study Discontinuation form ; Axitinib end date reported on the Study Discontinuation form ; Last visit date reported on the Study

TTF status and TTF time will be calculated as detailed below:

PFIZER CONFIDENTIAL

Page 12 of 41

Variable name	Definition

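### The SAP's TTF status rule does not match its any-reason definition: some axitinib stops are censored by default, and some study exits with no recorded stop count as failures

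*SAP*

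**What the plan says.** Definition. SAP 6.1.1 defines TTF under axitinib, and again TTF for the sunitinib-axitinib sequence, as ending at axitinib discontinuation, "whatever the reason for discontinuation and whatever the following therapeutic strategy". Protocol 8.7.1 says "whatever the reason for discontinuation is and whatever the following therapeutic strategy" for axitinib TTF and uses the death date if the patient dies while still treated. Its sequence definition does not carry the any-reason phrase.

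Status rule, identical for both endpoints in SAP 6.1.1:
- Case 1: "Axitinib discontinued due to Progression, Intolerability or Death (cf. CRF page 35").
- Case 2: "Study Discontinuation for any reason except lost to follow-up or patient's request whereas last treatment received is Axitinib (cf. CRF page 37").
- Default: "In all other cases, patient will be censored for the TTF analysis (TTF status = 0").
- Note: other reasons for stopping axitinib or leaving the study "will be reviewed at time of DRMs in order to decide whether corresponding cases should be censored or not for TTF analysis".

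Timing. A case 2 exit is an event at the last visit date "if case n°2 described above is reported and reason for study discontinuation is not 'death' and Axitinib status at last visit is 'ongoing". It is dated at death "if case n°2 described above is reported and reason for study discontinuation is 'death". Where only the month and year of the axitinib end are known, the day is set to 01. Censored patients are censored at the later of the last axitinib visit and the last visit on the study discontinuation form. Under SAP 6.1.2, TSF takes the sequence TTF status.

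Forms (Protocol Annex 1). The axitinib follow-up form, as annexed, shows three discontinuation reasons: progression, intolerability and death. The study discontinuation form asks, for a patient on the drug at the previous visit, whether the drug was ongoing or discontinued, with an end month and a reason.

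**The concern.** An any-reason definition makes the stop itself the event. The status rule asks instead why the drug was stopped, on which page this was recorded, and why the patient left the study. The same recorded stop can therefore be an event in one patient and a censored time in another, and a patient with no recorded stop can be an event.

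TTF accounts for two of the four primary endpoints. The study is descriptive and the SAP (4.2) plans no test, so the reported median is itself the result. If the rule stands, that median is not the time to axitinib discontinuation for any reason, and part of the classification rests on review decisions taken case by case without a stated criterion.

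**Working it through.** **1. Definition against default rule**

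| Situation | Any-reason definition | SAP default |
|---|---|---|
| (a) Axitinib stopped for another reason, no qualifying study exit | Event at the stop | Censored; data review may change it |
| (b) Lost to follow-up or own request; stop recorded only on the study discontinuation form | Event at the stop | Censored at a last visit, which can be later than the stop |
| (c) Exit to another study, axitinib ongoing at last visit | No recorded stop, so no event | Event at last visit; data review may possibly change it |
| (d) Exit to another study, axitinib discontinued on the same form | Event at the stop | Event at the end date |

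Rows (b) and (d) can hold the same drug information and differ only in the reason for leaving. Row (b) includes stops for progression or intolerance, because case 1 reads only the axitinib page. SAP 6.3.1 lists other reasons for axitinib discontinuation, so row (a) is anticipated.

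**2. The plan's own figure.** Protocol 8.5 states an accuracy of 5.2% for median PFS and TTF with 350 patients. Half-width of the 95% interval for S(t) at the median: 1.96 × √(0.25/350) = 0.0524. It reproduces. It describes sampling error only and does not cover misclassified events.

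**3. Stops left censored.** Let f be the share of axitinib stops that stay censored after review, constant over time and censored at the stop. The apparent hazard is (1−f)h(t), so the apparent S is S^(1−f). At the true median:
- f = 5%: 0.5^0.95 = 0.518, +1.8 points
- f = 10%: 0.5^0.90 = 0.536, +3.6 points
- f = 20%: 0.5^0.80 = 0.574, +7.4 points

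Under constant hazard the median is multiplied by 1/(1−f): 1.053, 1.111 and 1.250. If review turns half of an initial 10% into events, f becomes 5% and the excess falls to about 5%. Censoring later than the stop adds to it: with f = 10% and an assumed median of 6.5 months (a PFS figure from Protocol 8.5; no TTF figure is given), a delay of 1 month gives +12.3% and 6 months +16.6%.

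**4. Ongoing exits counted.** Let g be the share of counted endings that are ongoing exits with no true stop. With stop hazard h and exit hazard e, g = e/(h+e), so the median is multiplied by h/(h+e) = 1−g: 0.98, 0.95 and 0.90 for g = 2%, 5% and 10%.

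A Kaplan-Meier simulation (200,000 patients per setting, exponential times) agrees. With f = 10% alone the median is 7.24 against 6.52 months, ratio 1.11. With an exit hazard of one tenth of the stop hazard (g = 0.1/1.1 = 9.1%) it is 5.93 against 6.52, ratio 0.91.

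**5. Both together.** The factor is (1−g)/(1−f). For f = 10%, g = 5%: 0.95/0.90 = 1.056. For f = 5%, g = 10%: 0.90/0.95 = 0.947. For f = g the two errors cancel.

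**6. Minor points.** A death exit with axitinib as last treatment and no case 1 record is dated at death even if the form's death block shows an earlier axitinib end: the discontinued line excludes deaths, and the rule taking the earliest date needs more than one case. If 2% of patients were dated 3 months late (both assumed, median 6.5 months), the median would rise by about 1%. Separately, if axitinib starts on day d and ends in the same month, the forced day 01 gives 1 − d + 1 = 2 − d days: 1, 0 and −1 for d = 1, 2 and 3.

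**The case against.** The best defence is that case 1 mirrors the form. On the annexed axitinib page it covers every reason that can be ticked, so group (a) may be nearly empty, and the note sends other reasons to data review. Group (b) is also narrow: the patient must have been on axitinib at the previous visit, then leave by one of two routes, with a stop on that form and no case 1 record. An exit to another study may well involve an axitinib stop, in which case an event near the last visit is roughly right. The protocol leaves detailed definitions to the SAP and lets the SAP modify its plans.

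Much of this stands, and it limits the claim. Four stronger readings are tempting, and the documents do not support them:
- That the SAP's PFS rule shows other-reason stops are expected. It speaks of stopping for reasons other than progression, which includes intolerability, already a case 1 event. Only SAP 6.3.1 and the review note point to other reasons.
- That exits to another study are fixed as events. The note names study discontinuation reasons and can be read to reach them.
- That the protocol defines both TTF endpoints as any-reason. It does so for axitinib TTF; for the sequence, only the SAP does.
- That a protocol amendment is plainly required. Protocol 8.7 asks for one for major modifications, and whether this is major is a judgement.

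The defence does not remove the mismatch. Under an any-reason definition there is nothing to decide about whether a stop counts, yet the note leaves exactly that open, gives no criterion and does not clearly reach group (b).

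**Conclusion.** The mismatch between definition and status rule is real on the text of SAP 6.1.1, for both TTF endpoints and, through the inherited status, for TSF. It should be fixed before data review. Its size and net direction are unknown: the documents give neither f nor g, and the number of other-reason stops depends on the final eCRF. The figures of about +11% for f = 10% and −10% for g = 10% are illustrations. They assume constant hazard, a constant f with censoring at the stop, and, for g, that none of the ongoing exits hides a true stop. A reader might take the ranges shown as upper limits; nothing in the documents bounds them. Death dating and the forced day 01 are small derivation faults and do not drive the conclusion.

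**What to change.** For both TTF endpoints, with TSF following:
- Status 1: any recorded permanent axitinib discontinuation, whatever the reason and on whichever form, at the recorded stop date; or death while on axitinib, at the death date.
- Status 0: otherwise, at the last date axitinib is documented as ongoing.
- Query exits to another study for an axitinib stop date, and count a documented stop as an event.
- Where axitinib ended before death or study exit, use the recorded end date, including the one in the death block of the study discontinuation form.
- Keep imputed end days no earlier than the axitinib start date.
- Limit data review to whether and when axitinib stopped, not whether a stop counts.

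The cost is SAP wording, derivation code and a few data queries. The reported median may move either way.

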6. STUDY DISCONTINUATION

Study Discontinuation
Please complete this form in case of study discontinuation during the study at any time of the study for any reason
Date of study discontinuation : / / (DD/MMYYYYY)
Reason for study discontinuation
☐ Subject did not show up again (e.g. moved away), "Lost to follow-up",
☐ Subject was enrolled in another clinical study
☐ Subject's request / withdrawal of subject's consent
□ Death
☐ Other, please specify :
If the patient is alive at study discontinuation:
Date of the last visit with the patient at the site / / (DD/MM/YYYY)
If the patient was treated with Sunitinib / Axitinib* at the previous visit :
Sunitinib /Axitinib* status at the last visit date : □ Ongoing □ Discontinued
End date / (MM/YYYY)
Reason for discontinuation
□ Progression disease Date : ᆜᆜ / ᆜᆜ / ᆜᆜ ᆜ
□ Intolerance
□ other
*: name to be selected according to the line of the treatment
In case of death 2 Voc No.
In case of death ?
Date of death
Cause tumor-related other cause
If the patient was treated with Sunitinib / Axitinib* at the previous visit:
Sunitinib / Axitinib* status at the date of death : □ Ongoing □ Discontinued End date □□ / □□□□ (MM/YYYY)
Reason for discontinuation
☐ Progressive disease Date : ☐ / ☐ / ☐ ☐ Intolerance
□ other
*: name to be selected according to the line of the treatment
. Have to be delected describing to the line of the treatment

ADONIS CRF

Subject ID:

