	Discontinuation form} - Start date of Axitinib + 1) / 30.44 , if more than 1 case described above is reported
	Else, the time to treatment failure will be censored as follows:
	• (Maximum of { Date of last Axitinib follow-up visit ; Last visit date reported on the Study Discontinuation form whereas last treatment received is Axitinib } - Start date of Axitinib + 1)/30.44
	Note : Start date of Axitinib will be the one reported at time of Axitinib initiation visit (cf. CRF page 25 " Therapy started with Axitinib in 2nd line on ")

- Time to Treatment Failure (TTF) for the sequence Sunitinib-Axitinib

The TTF will be defined as the time when the patient receives the first dose with SU in 1st line to the time of AXI 2nd line treatment discontinuation (date completed by the physician), whatever the reason for discontinuation and whatever the following therapeutic strategy.

Variable name	Definition
TTF status	Patient will not be censored for the TTF analysis (TTF status = 1) in the following cases:
	 Axitinib discontinued due to Progression, Intolerability or Death (cf. CRF page 35)
	 Study Discontinuation for any reason except lost to follow-up or patient's request whereas last treatment received is Axitinib (cf. CRF page 37)
	In all other cases, patient will be censored for the TTF analysis (TTF status = 0).
	Note: Other reasons for Axitinib discontinuation as well as other reason for study discontinuation (whereas last treatment received is Axitinib) will be reviewed at time of DRMs in order to decide whether corresponding cases should be censored or not for TTF analysis

TTF status and TTF time will be calculated as detailed below:

Variable name	Definition
TTF time	The time to treatment failure will be calculated in months as:
(months)	• (Date of progression/intolerability or death reported at time of Axitinib discontinuation - Start date of Sunitinib + 1) / 30.44, if case n°1 described above is reported
	• (Date of death reported on the Study Discontinuation form - Start date of Sunitinib + 1) / 30.44, if case n°2 described above is reported and reason for study discontinuation is 'death'
	• (Axitinib end date reported on the Study Discontinuation form - Start date of Sunitinib + 1) / 30.44, if case n°2 described above is reported and reason for study discontinuation is not 'death' and Axitinib status at last visit is 'discontinued'

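### TTF is dated at death for patients whose axitinib had already stopped, if the only TTF event recorded is study discontinuation for death

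*SAP*

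**What the plan says.** **Definition.** SAP 6.1.1 runs TTF under axitinib from the first axitinib dose "to the date of AXI discontinuation (date completed by the physician), whatever the reason for discontinuation". Protocol 8.7.1 defines it the same way and adds one rule on death: "In case of death while the patient is still treated with AXI, date of death will be considered as date of discontinuation".

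**Events.** The SAP counts two cases as events:
- Case 1: "Axitinib discontinued due to Progression, Intolerability or Death (cf. CRF page 35").
- Case 2: "Study Discontinuation for any reason except lost to follow-up or patient's request whereas last treatment received is Axitinib".

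**Dates.** Each TTF table then assigns the end date:
- Case 1: the date on the axitinib discontinuation page.
- Case 2, reason death: "Date of death reported on the Study Discontinuation form - Start date of Axitinib + 1) / 30.44". The sequence table has the same rule from sunitinib start: "Date of death reported on the Study Discontinuation form - Start date of Sunitinib + 1".
- Case 2, axitinib end date from the Study Discontinuation form: only if "reason for study discontinuation is not 'death' and Axitinib status at last visit is 'discontinued".
- Case 2, last visit date: only if the reason is not death and axitinib is ongoing.
- More than one case reported: the minimum of the listed dates.

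TSF takes its status from the sequence TTF, and its time is that TTF less the interval between sunitinib and axitinib.

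**Data collected.** In its death block, the Study Discontinuation form (Protocol Annex 1, CRF section 6) asks for axitinib "status at the date of death", ongoing or discontinued, with a month/year end date. It asks this only if the patient was on the drug at the previous visit.

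**The concern.** The protocol's condition that the patient is still on treatment is missing from the SAP's date rule for case 2 deaths, and the rule that reads the axitinib end date excludes deaths. A patient who meets case 2 alone, with reason death, is therefore dated at death even when the form shows that axitinib had stopped earlier. For that patient the endpoint is survival from the start of axitinib (or of sunitinib), not treatment duration.

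Both TTFs are primary endpoints and TSF inherits the error. It can only lengthen the times. In an uncontrolled descriptive study, where the median is itself the result, that overstates how long patients stay on treatment.

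**Working it through.** The plan states no figure for this rule, so there is none to reproduce. The check has two parts.

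**1. Apply the rules to test patients.** Time = (end date − start date + 1) / 30.44. The dates are illustrative: axitinib starts 1 January 2016, stops 1 July 2016 (182 days later), death 1 May 2017 (486 days later).

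- Stop: (182 + 1) / 30.44 = 6.01 months.
- Death: (486 + 1) / 30.44 = 16.00 months.

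| Patient | Cases met | SAP gives | Protocol 8.7.1 gives |
|---|---|---|---|
| A: progression or intolerability stop on the axitinib page, no later drug, then death | 1 and 2, so the minimum applies | 6.01 | 6.01 |
| B: on axitinib until death | 2 (reason death) | 16.00 | 16.00 |
| C: axitinib stopped, no case 1 stop recorded, then death | 2 only (reason death) | 16.00 | 6.01 |
| D: case 1 stop, later drug, then death | 1 only | 6.01 | 6.01 |

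Only patient C is misdated, by 16.00 − 6.01 = 9.99 months, which is the whole interval from stop to death.

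**Who is patient C?** The documents allow two routes.
- *Stop between visits.* The stop appears only on the Study Discontinuation form. The patient was on axitinib at the previous visit, and axitinib visits are expected about every 4 weeks (Protocol 8.2), so the gap is probably short.
- *Stop for another reason.* SAP 6.3.1 lists other reason among the axitinib discontinuation reasons, but the printed axitinib discontinuation page offers only progression, intolerability and death. Such a stop is not case 1. If no further drug follows and the patient dies during six-monthly follow-up, the gap can be longer.

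**2. Illustrate the effect on the median.** Assumptions:
- Axitinib treatment time is exponential with median 6.5 months, using the investigator-assessed AXIS PFS from Protocol section 6 as a proxy.
- A share f of patients is of type C.
- Their stop-to-death gap is exponential and independent of treatment time.

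With a = ln 2 / 6.5 and b the rate of the gap (1/mean, or ln 2/median),

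S(t) = (1 − f)·e^(−at) + f·[b·e^(−at) − a·e^(−bt)] / (b − a),

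and the reported median solves S(t) = 0.5.

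| f | Gap mean 1 month | Gap median 6 months | Gap median 12 months |
|---|---|---|---|
| 5% | 6.5 + 0.06 | 6.83 | 6.90 |
| 10% | 6.5 + 0.11 | 7.17 | 7.34 |
| 20% | 6.5 + 0.22 | 7.92 | 8.37 |

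The first column fits stops between visits. The other two apply only if most affected patients are other-reason stops with long survival afterwards.

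**The case against.** A reader might infer that every death recorded as the study discontinuation reason is dated at death even if axitinib had stopped earlier. The documents do not support that. A stop on the axitinib page for progression or intolerability makes the patient case 1 as well as case 2, and the minimum rule takes the stop date. If another drug followed, case 2 does not apply. These routes (patients A and D) are handled correctly.

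Further points on the other side:
- *The minimum rule might be read more loosely*, with case meaning any reported date, which would rescue patient C. But the tables number only cases 1 and 2, and the bullets on the death date and the axitinib end date exclude each other by reason.
- *Data review meetings look at other reasons for stopping.* The SAP note does send these patients to review, but only to decide whether to censor them. It sets no date.
- *The effect may be very small.* This stands as a limit on size. The share affected is unknown, and for stops between visits the gap is probably short. The plan's 5.2% accuracy (Protocol 8.5) corresponds to roughly ±1 month around a 6.5-month exponential median: −ln(0.552)/a = 5.57 and −ln(0.448)/a = 7.53.
- *The status field on the form does not serve deaths in long-term follow-up*, because it is asked only of patients on the drug at the previous visit. This stands, so the correction cannot rely on that field alone.
- *The study is descriptive and plans no test of TTF.* True, and it lowers the severity. It does not remove a conflict between the SAP's date rule and the endpoint definition in both documents.

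**Conclusion.** The point holds in a narrow form. For deaths that meet TTF case 2 only, with axitinib already stopped, the SAP dates both primary TTFs at death and ignores the axitinib end date, contrary to Protocol 8.7.1 and to its own definition. TSF inherits the error. Each such patient is overstated by the full stop-to-death interval, and the direction is always upward.

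The effect on the median cannot be derived, since the documents give neither the share affected nor the gap. The shifts above are illustrations under assumed values, not estimates. They run from under 0.1 month (5% affected, mean gap 1 month) to nearly 2 months (20% affected, median gap 12 months), and nothing in the documents shows that the upper end is likely. This is a drafting gap that should be closed before analysis, not a flaw that undermines the primary endpoints.

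**What to change.** In both TTF tables of SAP 6.1.1:

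1. Use the date of death only if axitinib was ongoing at death. Otherwise use the earliest axitinib stop date recorded on any form, whatever the study discontinuation reason. Equivalently, apply the minimum rule to all recorded stop and death dates, not only when more than one case is reported. TSF then follows without further change.
2. For other-reason stops, where the printed axitinib discontinuation page has no date field, name a fallback date before data review.
3. Where another form gives a full stop date, prefer it to the month/year end date on the Study Discontinuation form.

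**Cost.** A wording change in two tables and the matching program lines. Patients who died on axitinib, had a recorded case 1 stop or received a later drug are unaffected. The real downside is precision. The SAP forces the day of a month-only end date to 01, which can shorten TTF by up to 30 days. For a stop between visits that may be as large as the bias removed, which is the reason for step 3.

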	Note: as only month and year of Axitinib end are reported in such cases, day of Axitinib end will automatically be "forced" to 01
	• (Last visit date reported on the Study Discontinuation form - Start date of Sunitinib + 1) / 30.44, if case n°2 described above is reported and reason for study discontinuation is not 'death' and Axitinib status at last visit is 'ongoing'
	 (Minimum of {Date of progression/intolerability or death reported at time of Axitinib discontinuation ; Date of death reported on the Study Discontinuation form ; Axitinib end date reported on the Study Discontinuation form ; Last visit date reported on the Study Discontinuation form} - Start date of Sunitinib + 1) / 30.44, if more than 1 case described above is reported
	Else, the time to treatment failure will be censored as follows:
	 (Maximum of { Date of last Axitinib follow-up visit ; Last visit date reported on the Study Discontinuation form whereas last treatment received is Axitinib } - Start date of Sunitinib + 1) / 30.44
	Note: Start date of Sunitinib will be the one reported:
	- at time of Sunitinib initiation visit for patients enrolled at SU initiation (cf. CRF page 11 "Therapy started with Sunitinib in 1st line on")
	- at time of Axitinib initiation visit for patients enrolled at AXI initiation (cf. CRF page 26 "Therapy started with Sunitinib in 1st line on")

6.1.2 Secondary Endpoints

- Time to Strategy Failure (TSF) for the sequence Sunitinib-Axitinib

The TSF will be defined as the time from when the patient receives the first dose with SU in first line to the time of AXI 2nd line treatment discontinuation (date completed by the physician) without the time between discontinuation of SU and start of the 2nd line AXI treatment.

TSF status will be the same as TTF status for the sequence Sunitinib-Axitinib.

TSF time will be equal to:

- For patients enrolled at SU initiation : TTF time (Start date of Axitinib reported at time of Axitinib initiation visit Date of progression/intolerability/death reported at time of Sunitinib discontinuation)
- For patients enrolled at AXI initiation : TTF time (Start date of Axitinib reported at time of Axitinib initiation visit Date of Sunitinib end reported at time of Axitinib initiation visit*)

*cf. CRF page 26 "Therapy with Sunitinib in first line; therapy discontinuation on"

- Overall Survival (OS) for the sequence Sunitinib-Axitinib

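### Setting the axitinib end day to 01 shortens TTF by about half a month in each affected record and can give zero or negative TTF under axitinib; the cohort effect is probably small

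*SAP*

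**What the plan says.** SAP section 6.1.1 counts two kinds of TTF event. Case 1 is axitinib stopped for progression, intolerability or death, timed by "Date of progression/intolerability or death reported at time of Axitinib discontinuation - Start date of Axitinib + 1) / 30.44, if case n°1". Case 2 is "Study Discontinuation for any reason except lost to follow-up or patient's request whereas last treatment received is Axitinib".

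Within case 2, if "reason for study discontinuation is not 'death' and Axitinib status at last visit is 'discontinued", the end date comes from the Study Discontinuation form and the time is "Axitinib end date reported on the Study Discontinuation form - Start date of Axitinib + 1) / 30.44". Here the SAP adds that "as only month and year of Axitinib end are reported in such cases, day of Axitinib end will automatically be" forced to 01. The same note stands in the table for the SU-AXI sequence TTF, and TSF is derived from that TTF.

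If more than one case is reported, the SAP takes the "Minimum of {Date of progression/intolerability or death reported at time of Axitinib discontinuation" and the other candidate dates, among them the axitinib end date on the Study Discontinuation form.

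The CRF (protocol Annex 1) explains the rule. The Study Discontinuation form (section 6) collects the axitinib end as month and year, but the last visit to the day. The axitinib follow-up page (section 4.2) collects the date of stopping for progression, intolerability or death to the day.

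**The concern.** Day 01 is the earliest date the partial record allows, so every error shortens the time or is zero; errors cannot cancel across patients. Neither the TTF tables nor SAP section 7 on missing values sets a floor at the axitinib start date. An imputed stop can therefore precede the start, and this falls on the shortest-treated patients. A zero or negative time is not a meaningful Kaplan-Meier event time, and the SAP does not say how it would be handled.

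The minimum rule adds a second problem. The form's end date needs a day before it can be compared with complete dates, and 01 is the only day the SAP supplies. In a tie on month, the imputed date then beats any observed date other than the 1st. TTF is a primary endpoint, so its dating rule should neither produce impossible values nor overwrite good data.

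**Working it through.** **The plan's own figure.** The documents give no figure for the effect of this rule. The nearest is the precision in protocol section 8.5, Table 2: 1.96 × √(0.25/350) = 0.0524, which matches the stated 5.2% for 350 SU-AXI patients.

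**Shift per affected record.** Shift = (true day - 1)/30.44 months. Averaged over all calendar days from 01 Feb 2014 to 30 Apr 2021 (the planned data collection period), with the true stop equally likely on any day:
- mean 14.7 days; 14.7/30.44 = 0.48 month
- range 0 to 30 days; 30/30.44 = 0.99 month

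With day 15 instead, the true day is on average 0.7 day later than the imputed one, and the error is at most 16 days.

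**Start and stop in the same month.** Imputed TTF under axitinib = (1 - start day + 1)/30.44 = (2 - start day)/30.44:

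| Start day | Imputed TTF (months) |
|---|---|
| 2 | 0 |
| 3 | -1/30.44 = -0.03 |
| 20 | -18/30.44 = -0.59 |
| 31 | -29/30.44 = -0.95 |

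Example: start 10 March, true stop 28 March. True TTF is 19/30.44 = 0.62 month; imputed TTF is -8/30.44 = -0.26 month.

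For the sequence TTF, a non-positive value would need sunitinib to start in the month axitinib ends, which is practically excluded.

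**Minimum rule.** Illustration: the axitinib page gives a stop on the 24th, and the Study Discontinuation form gives the same month and year. The minimum picks the imputed 1st, and the record loses 23 days (23/30.44 = 0.76 month) although the exact date is known.

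**Cohort effect.** The share of SU-AXI patients timed by the imputed date is not given, so it is an assumption here. Fall in mean TTF = 0.48 × share:

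| Assumed share | Fall in mean TTF (months) |
|---|---|
| 5% | 0.02 |
| 10% | 0.05 |
| 20% | 0.10 |
| 50% | 0.24 |

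A simulation of 1,000,000 patients used exponential TTF with assumed medians of 4.8, 6.5 and 8 months. The 6.5 is the investigator-assessed PFS after sunitinib in the AXIS trial (protocol section 6), a proxy because no TTF median is given. Results:
- the median falls by 0.03 to 0.07 month at a 10% share, by 0.10 at 20%, and by nearly half a month (0.46 to 0.49) only when every patient is affected
- 3.8% to 6.3% of affected records are negative
- at the 6.5-month median, about 0.8 negative records are expected among 350 patients at a 5% share and 1.6 at 10%

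**Against the planned precision.** For an exponential curve with median 6.5 months, the slope at the median is 0.5 × ln 2/6.5 = 0.0533 per month. So ±0.0524 in S(t) is about 0.0524/0.0533 = ±1 month on the median.

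**The case against.** The strongest objection is that the rule is narrow. Case 1 stops carry complete dates. Once death, loss to follow-up and patient's request are removed from the form's list of reasons, only enrolment in another clinical study and 'other' remain. The form asks for the axitinib end date only if the patient was on treatment at the previous visit, which also limits how often the minimum rule meets two dates. The study is descriptive, has no decision rule for TTF, and the error does not flatter the drug. All of this stands, and it limits the size of the point.

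A reader might infer that the primary TTF as a whole is half a month too short, or about 8% of a 6.5-month median (0.5/6.5 = 7.7%). The documents do not support that. It divides a per-record shift by a cohort median, and would hold only if nearly every patient were timed by the form. The 6.5 months is also a PFS from another trial.

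It could also be said that the Data Review Meetings will resolve these cases. The TTF note sends other reasons for discontinuation to those meetings only to decide on censoring, not on dates. The remark that the calculation could be adapted stands in the PFS tables, not the TTF tables.

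**Conclusion.** The point holds for affected records, as a minor one. Day 01 shortens TTF by 0.48 month on average, always in the same direction, and sequence TTF and TSF carry the same shift. Zero or negative times concern TTF under axitinib only. An imputed date can displace an exact one where more than one case is reported.

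The per-record mean assumes stop days spread evenly over the month. The cohort effect depends on a share that the documents do not state. At assumed shares of 5% to 20% it is 0.02 to 0.10 month on the mean, well below the roughly ±1 month of planned precision on the median. The case for change is that the rule can yield impossible values and override observed data, not that it materially distorts the reported median.

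**What to change.** In both TTF tables of SAP section 6.1.1, replace the day-01 note as follows:

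- Impute day 15 of the reported month.
- Bound it below by the later of the axitinib start date and the last visit documenting axitinib as ongoing. Bound it above by the last visit date on the Study Discontinuation form, or by death. Day 15 alone is not enough, because a start after the 15th of the same month could still give a non-positive time. With the floor, the shortest possible TTF under axitinib is 1/30.44 = 0.03 month.
- In the minimum rule, let any complete date take precedence over an imputed one.
- Report the number of patients timed by an imputed date.

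TSF follows from the sequence TTF and needs no separate rule. The cost is SAP wording and a few lines of code; no CRF change or new data collection is needed.
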